## **8.5.2. Secondary Analyses**

The secondary endpoint of COVID-19 related hospitalization or all-cause death by Day 14, COVID-19 related MAVs (medical visits attended in person by the participant and a health care professional) or death by Day 28, and COVID-19 related MAVs (medical visits attended in person by the participant and a health care professional) or death by Day 14 will be analyzed similarly as in the primary analysis. The all-cause mortality at Day 28 will be compared between the 2 treatment groups using a Fisher exact test. The proportion of participants hospitalized by Day 28 and the proportion of participants progressing to requiring oxygen supplementation by Day 28 will be estimated using the Kaplan-Meier method and compared between the 2 treatment groups using a log-rank test. Other endpoints of interest related to proportion of participants will be compared between treatment groups using a chi-square test or Fisher exact test. Endpoints that are measured as time to first event will be compared between treatment groups using the log-rank test and continuous endpoints will be compared between treatment groups using a Wilcoxon rank sum test or analysis of variance model.

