### **3. GENERAL CONSIDERATIONS FOR DATA ANALYSES**

Analysis results will be presented using descriptive statistics. For categorical variables, the number and percentage of participants in each category will be presented; for continuous variables, the number of participants (n), mean, standard deviation (SD) or standard error (SE), median, first quartile (Q1), third quartile (Q3), minimum, and maximum will be presented.

All statistical tests will be 2-sided and performed at the 5% significance level unless otherwise specified.

By-subject listings will be presented for all participants in the All Randomized Analysis Set and sorted by subject ID number, visit date, and time (if applicable). Data collected on log forms, such as AEs, will be presented in chronological order within the participant. The treatment group to which participants were randomized will be used in the listings. Age, sex at birth, race, and ethnicity will be included in the listings, as space permits.

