## **3.3. Strata and Covariates**

Participants will be randomly assigned to treatment groups via the interactive voice or web response system (IXRS) in a 1:1 ratio using a stratified randomization schedule. Stratification will be based on the following variables:

- Region: US vs. ex-US
- Participant’s age: < 60 vs  $\geq$  60 years
- Resident of skilled nursing facility: Yes vs. No

Stratification discrepancies will be reviewed and assessed. The values recorded in the clinical database will be used for analyses in case there are discrepancies between the IXRS and the clinical database. Based on the assessment of stratification discrepancies, a sensitivity analysis of the primary endpoint may be performed.

The primary efficacy endpoint will be evaluated in a stratified analysis based on the same 3 factors used for randomization, as specified in Section 6.1.3. In addition, observed imbalances between treatment groups in other baseline characteristics may be considered as covariates in sensitivity analyses of efficacy endpoints.

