#### 6.1.3. Primary Analysis of the Primary Efficacy Endpoint

The hazard ratio of COVID-19 related hospitalization or all-cause death between the two treatment groups will be estimated using a Cox model with stratification factors as covariates.

If a participant prematurely discontinues from the study prior to Day 28 or the hospitalization status is missing, the participant is censored at last study date or day 28 whichever is earlier. If a participant has a COVID-19 related hospitalization first and then dies, then date of the COVID-19 related hospitalization and status will be used for the primary analysis for this participant. If a participant has a non COVID-19 related hospitalization first and then dies without experiencing a COVID-19 related hospitalization, then date of the death and status will be used for the primary analysis for this participant.

The hazard ratio, p-value, 95% CI for the hazard ratio from Cox model, and proportion of COVID-19 related hospitalization or all-cause death at Day 28 from Kaplan-Meier estimate will be provided.

The FAS will be the primary analysis set for efficacy endpoint evaluation. The primary endpoint may be analyzed for each of the subgroups defined in Section 3.3.

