### 6.2.1. Analysis of Secondary Endpoints

The FAS will be the primary analysis set for secondary endpoints. The mFAS will be used for secondary endpoints of composite endpoint of COVID-19 related MAVs or death.

All-cause mortality by Day 28 will be compared between the 2 treatment groups using the Fisher exact test. If a participant prematurely discontinues from the study prior to Day 28 or the Death status is missing, the participant will not be included in the analysis.

The secondary endpoint of COVID-19 related hospitalization or all-cause death by Day 14, COVID-19 related MAVs or death by Day 28, and COVID-19 related MAVs or death by Day 14 will be analyzed using the same method as used for the primary endpoint, described in Section 6.1.3.

The proportion of participants hospitalized (COVID-19 related) by Day 28 will be estimated using the Kaplan-Meier method and compared between the 2 treatment groups using a log-rank test. Hazard ratio and two-sided 95% CI estimated using the Cox regression with baseline stratification factors as covariates will be provided.

Number and percentage of participants progressing to requiring oxygen supplementation by Day 28 will be summarized and compared between treatment groups using the Fisher Exact test. Participants discontinued from the study before progressing to requiring oxygen supplementation will be considered as not requiring oxygen supplementation.

The Kaplan-Meier product limit method will be used to estimate and log-rank test will be used to compare treatment groups for the time to alleviation of baseline COVID-19 symptoms. Hazard ratio and two-sided 95% CI estimated using the Cox regression with baseline stratification factors as covariates will be provided. Number and proportion of participants with worsening after alleviation of baseline COVID-19 symptoms will be summarized.

Time-weighted average change in SARS-CoV-2 viral load from baseline to Day 7 will be summarized by treatment groups and compared between treatment groups using an ANCOVA model with baseline viral load as covariate, the analysis will be based on the Virology Analysis Set.

CC1

[REDACTED]

[REDACTED]

[REDACTED]

[REDACTED]

[REDACTED]

[REDACTED]

[REDACTED]

[figure not shown]
[REDACTED]

[REDACTED]

CCI

CCI

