  - i) Positive = any numeric result or “<LLOQ SARSCoV2 detected” - LLOQ could vary by sample type

- ii) Negative = “No SARS-CoV2 detected”
- iii) Inconclusive = “Inconclusive”
- c) For Negative SARS-CoV2 confirmation, “Inconclusive” SARS-CoV2 result will not be considered as missing thus a “Negative” followed by a “Inconclusive” is NOT confirmed.
- d) 2 negative results from the same day do not equal confirmation.
- e) if last PCR sample is negative for participants completed the study or for participant withdrawn early from the study, then one negative PCR of last sample is considered as confirmed negative.
- f) Categorical SARS-CoV2 and SARS-CoV2 negative summary will be separated out by sample type. There will be no combined Positive or negative category using 2 or more sample types.

25) SAS code for Cox model with Covariates

```
proc phreg;
class trt01p (ref="Placebo to match RDV") strat1 strat2 strat3;
model aval*cnsr(1) = trt01p strat1 strat2 strat3 /risklimits = wald;
ods output ParameterEstimates=Est1 ModelANOVA = pvout1;
run;
```

Hazard ratio is the hazardratio, 95% Cis are HRLowerCL and HRUpperCL where Parameter = “TRT01P” from EST1 dataset; P-value is ProbChiSq where Effect = “TRT01P” from pvout1 dataset.

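### For two exploratory endpoints (COVID-19 hospitalization and time to symptom alleviation) the p-value comes from a log-rank test with no strata named and the interval from an adjusted Cox model, so the two can disagree near p = 0.05

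*SAP*

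**What the plan says.** **Hospitalization by Day 28 (SAP 6.2.1).** The proportion is estimated by Kaplan-Meier and "compared between the 2 treatment groups using a log-rank test". The next sentence reads: "Hazard ratio and two-sided 95% CI estimated using the Cox regression with baseline stratification factors as covariates will be provided".

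**Time to alleviation (SAP 6.2.1).** The "log-rank test will be used to compare treatment groups for the time to alleviation of baseline COVID-19 symptoms". The same sentence about the Cox hazard ratio and CI follows. For neither endpoint does the SAP ask for a Cox p-value.

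**Primary endpoint (SAP 6.1.3).** "The hazard ratio, p-value, 95% CI for the hazard ratio from Cox model" are all reported, so test and interval share one model. The three composite secondary endpoints use the same method. The code in SAP Appendix 2, item 25, contains "trt01p strat1 strat2 strat3 /risklimits = wald" and so gives Wald limits.

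**Use of strata (SAP 3.3).** "The primary efficacy endpoint will be evaluated in a stratified analysis based on the same 3 factors used for randomization". No such statement is made for other endpoints.

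**Protocol 8.5.2.** The proportion hospitalized "will be estimated using the Kaplan-Meier method and compared between the 2 treatment groups using a log-rank test". A general sentence in the same section assigns the log-rank test to time-to-first-event endpoints. Neither mentions strata, and no adjusted Cox estimate is specified for these two endpoints.

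**Level and status.** SAP section 3: "All statistical tests will be 2-sided and performed at the 5% significance level unless otherwise specified". SAP 3.5 classes every efficacy endpoint other than the primary as exploratory, tested at 5% without multiplicity adjustment.

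**The concern.** For these two endpoints the significance verdict and the interval come from different procedures. Only the interval takes account of region, age group and skilled-nursing residence, by which the trial randomized. The report could therefore show p below 0.05 beside a 95% CI that includes 1, or the reverse, and the SAP does not say which result then governs.

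One consequence follows from the text alone. COVID-19 hospitalization differs from the primary composite only through deaths not preceded by a COVID-19 hospitalization. If no such death occurs and censoring is the same, the two endpoints have identical data. The plan would then print the same hazard ratio and CI twice with two different p-values, one from Cox and one from log-rank. The documents do not give the number of deaths, so this is conditional.

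What is at stake is the consistency and readability of two secondary results.

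**Working it through.** **1. Test and interval side by side**

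| Endpoint | p-value | HR and 95% CI |
|---|---|---|
| Primary composite; three composite secondary endpoints | adjusted Cox | adjusted Cox |
| COVID-19 hospitalization by Day 28 | log-rank, no strata named | adjusted Cox |
| Time to alleviation | log-rank, no strata named | adjusted Cox |

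Reading the log-rank test as unstratified is an inference from silence, but a reasonable one. SAP 3.3 limits the stratified analysis to the primary endpoint, and SAP 6.1.4 names the strata explicitly for its CMH test.

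**2. The plan's own figure.** The documents give no figure on this point. The nearest is the stated power above 90% for the primary endpoint (Protocol 8.9, SAP 1.3), checked here to confirm the planning inputs.
- HR = ln(1 − 0.066) / ln(1 − 0.12) = 0.5341 (stated: 0.534).
- Events = 1264 × 0.95 × 0.093 = 111.7.
- Power = Φ(√(111.7 × 0.25) × |ln 0.5341| − 1.96) = 91.2%. It reproduces.

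**3. Why the two can differ.** The log-rank statistic is z = (O − E)/√V, a score statistic with no covariates. The planned interval is exp(b ± 1.96 × SE), with b from a model that also contains three factors. Two things differ: adjustment, and the type of statistic (score against Wald, including the treatment of same-day ties).

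**4. How often they differ.**
- *From the documents:* 584 randomized (SAP 2.1.1), 1:1 allocation, 12% placebo event rate, HR 0.534 and 5% dropout (SAP 1.3). The rate and HR are planning values for the composite, borrowed here for hospitalization.
- *Assumed:* prevalence of 30% (age 60 or over), 90% (US) and 3% (skilled nursing facility); prognostic HRs of 2, 1.5 and 3 for hospitalization and 0.6, 0.7 and 0.5 for alleviation, or all equal to 1; an alternative 5% placebo rate; 35% or 60% alleviated by Day 14; alleviation HR 1.3; exponential times rounded up to days; all 584 analysed.

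Each row is 1000 simulated trials. Disagreement means that the log-rank test is significant and the adjusted Cox Wald CI includes 1 (column A), or the reverse (column B).

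| Endpoint, base rate | HR | Factors prognostic | Disagree | A | B | Log-rank vs unadjusted Cox CI |
|---|---|---|---|---|---|---|
| Hospitalization, 12% | 1 | no | 1.3% | 0.9% | 0.4% | 0.5% |
| | 1 | yes | 1.7% | 1.0% | 0.7% | 0.5% |
| | 0.534 | no | 1.2% | 0.8% | 0.4% | 0.7% |
| | 0.534 | yes | 3.8% | 1.9% | 1.9% | 1.0% |
| Hospitalization, 5% | 1 | no | 0.8% | 0.4% | 0.4% | 0.1% |
| | 1 | yes | 1.1% | 0.8% | 0.3% | 0.6% |
| | 0.534 | no | 3.0% | 3.0% | 0.0% | 3.3% |
| | 0.534 | yes | 4.2% | 3.8% | 0.4% | 2.8% |
| Alleviation, 35% | 1 | no | 1.0% | 0.8% | 0.2% | 0.8% |
| | 1 | yes | 1.6% | 0.9% | 0.7% | 0.3% |
| | 1.3 | no | 2.4% | 1.8% | 0.6% | 1.2% |
| | 1.3 | yes | 5.5% | 3.3% | 2.2% | 1.5% |
| Alleviation, 60% | 1 | no | 0.7% | 0.6% | 0.1% | 0.7% |
| | 1 | yes | 2.3% | 1.3% | 1.0% | 0.6% |
| | 1.3 | no | 2.6% | 2.4% | 0.2% | 2.0% |
| | 1.3 | yes | 5.9% | 3.0% | 2.9% | 3.1% |

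The range is 0.7% to 5.9%. The Monte Carlo standard error is at most √(0.059 × 0.941 / 1000), about 0.7 points. Allocation was 1:1 overall but not stratified in the simulation, so chance imbalance in the factors is larger than under the plan, and the share due to adjustment is if anything overstated.

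**5. Which share is adjustment.** The last column removes adjustment, yet disagreement remains at 0.1% to 3.3%. In the sparse hospitalization scenario without prognostic factors (about 22 events) it accounts for all of it. Adjustment adds most where the factors are prognostic and there is a treatment effect: 1.0% rises to 3.8% for hospitalization at the 12% rate, and 1.5% to 5.5% for alleviation at the 35% rate.

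**6. After the fix.** The Wald test gives p < 0.05 exactly when |b/SE| > 1.96, which is exactly when b ± 1.96 × SE excludes 0. Disagreement is 0% by construction.

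**The case against.** The strongest reply is that nothing here is invalid. The protocol names the log-rank test, the SAP keeps it and adds an effect estimate, and each endpoint has one designated test and one designated estimate, so there is no choice between p-values. Both endpoints are exploratory, and other secondary analyses (Fisher tests, the viral-load ANCOVA) also leave out the strata. Replacing a protocol-named test after enrollment has stopped is a late change. If hospitalizations are few, a Wald test from a model with three covariates may be less stable than a log-rank test.

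Most of this stands, and it keeps the point minor. It does not remove the mismatch: SAP 3.5 still tests these endpoints at 5%, so a reader will see a significance verdict beside an interval from another model.

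Three stronger readings are tempting, and the documents do not support them:
- *The log-rank test inflates type I error or biases the result.* Leaving the strata out after stratified randomization makes a test at most slightly conservative. The power cost is also slight: in a separate simulation of alleviation (assumed n = 540, HR 1.25, strong covariate effects) power was 27.6% for log-rank and 28.9% for adjusted Cox.
- *Efficacy conclusions are at risk.* Efficacy is judged on the primary endpoint, where HR, CI and p-value share one model.
- *Missing strata cause the whole mismatch, so a stratified log-rank test would cure it.* Step 5 shows disagreement with no adjustment at all. Stratifying would reduce it but not remove it.

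**Conclusion.** The mismatch is real on the plain text and its consequence is small. For two exploratory endpoints the test ignores randomization factors that the interval uses, and near p = 0.05 the two can contradict each other. The size is about 1% to 6% of simulated trials: up to 4.2% for hospitalization and up to 5.9% for alleviation. These figures depend on prevalences, prognostic effects, alleviation rates and a low-event scenario that the documents do not give, so they indicate an order of magnitude and do not predict this trial's result. They also assume that the log-rank test is unstratified, which the SAP implies but does not state. The worst case is an inconsistent pair of numbers in the report.

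**What to change.** In SAP 6.2.1, for COVID-19 hospitalization by Day 28 and time to alleviation, take the treatment p-value from the covariate-adjusted Cox model that already supplies the hazard ratio and CI, as 6.1.3 does. Keep the log-rank test as a supportive analysis, state whether it is stratified, and list the change in 6.4, which at present records only the oxygen-supplementation change. Settle this before database finalization and unblinding.

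A log-rank test stratified by the three factors is a weaker alternative. It would respect the randomization groups, but the p-value and the CI could still disagree.

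The cost is one sentence and a line in 6.4, since the model is already fitted. The downsides are a small departure from the protocol's log-rank wording and a Wald test that may be less stable if hospitalizations are few. The supportive log-rank result covers both.

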	Lymphocytes	Decrease	Lymphocytes (Decreased)
	Neutrophils	Decrease	Neutrophils (Decreased)
	Platelets	Decrease	Platelets (Decreased)
	WBC	Decrease	WBC (Decreased)
Chemistry	Albumin	Decrease	Albumin (Decreased)
	Alkaline Phosphatase	Increase	Alkaline Phosphatase (Increased)
	ALT	Increase	ALT (Increased)
	AST	Increase	AST (Increased)
	Bicarbonate	Decrease	Bicarbonate (Decreased)
	Corrected Calcium	Increase	Corrected Calcium (Hypercalcemia)
	Corrected Calcium	Decrease	Corrected Calcium (Hypocalcemia)
	Creatine Kinase (CK)	Increase	Creatine Kinase (Increased)
	Creatinine	Increase	Creatinine (Increased)
	Creatinine Clearance	Decrease	Creatinine Clearance (Decreased)
	Lipase	Increase	Lipase (Increased)
	Magnesium	Decrease	Magnesium (Hypomagnesemia)
	Phosphate	Decrease	Phosphate (Hypophosphatemia)
	Serum Glucose (Fasting)	Increase	Serum Glucose (Fasting, Hyperglycemia)
Coagulation	Serum Glucose (Nonfasting)	Increase	Serum Glucose (Nonfasting, Hyperglycemia)
	Serum Glucose	Decrease	Serum Glucose (Hypoglycemia)
	Serum Potassium	Increase	Serum Potassium (Hyperkalemia)
	Serum Potassium	Decrease	Serum Potassium (Hypokalemia)
	Serum Sodium	Increase	Serum Sodium (Hypernatremia)
	Serum Sodium	Decrease	Serum Sodium (Hyponatremia)
	Total Bilirubin	Increase	Total Bilirubin (Hyperbilirubinemia)
	Uric Acid	Increase	Uric Acid (Hyperuricemia)
	Prothrombin Intl. Normalized Ratio (INR)	Increase	Prothrombin Intl. Normalized Ratio (Increased)
	Activated partial thromboplastin time (aPTT)	Increase	Activated partial thromboplastin time (Increased)

15) SAS code for ANCOVA:

```

ods output ParameterEstimates=out1 LSMeans=out2 LSMeanCL=out3
LSMeanDiffCL=out4;
proc glm data=dat1 plots=none;
class trt01pn;
model DAVG = trt01pn base / solution;
lsmeans trt01pn / stderr cl pdiff;
run;

```

```
ods output close; quit;
```

16) Symptom scores in the FLU-PRO questionnaire raw data start from 1 to n (total number of responses in a question), in the FLU-PRO user manual, symptom scores start from 0. In the analysis dataset, symptom scores will be re-mapped to match the scoring in the FLU-PRO user manual for proper calculation of total score and domain score.

17) FLU-PRO Total Score and Domain Score:

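### Optional free improvement: of the regression models visible in SAP 6.2.1, only the ANCOVA for time-weighted viral-load change to Day 7 (DAVG7) omits the three randomization factors

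*SAP*

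**What the plan says.** **DAVG7.** SAP 6.2.1 states that DAVG7 is "compared between treatment groups using an ANCOVA model with baseline viral load as covariate", in the Virology Analysis Set. The PROC GLM code in SAP Appendix 2, item 15 agrees: "class trt01pn", then "model DAVG = trt01pn base / solution", then "lsmeans trt01pn / stderr cl pdiff". Neither place includes a stratification factor.

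**Cox models in the same section.** The Day 14 composite of hospitalization or death and the two composites of medically attended visits or death "will be analyzed using the same method as used for the primary endpoint, described in Section 6.1.3"; that section specifies a Cox model with the stratification factors as covariates. COVID-19 related hospitalization by Day 28 is compared "using a log-rank test. Hazard ratio and two-sided 95% CI estimated using the Cox regression with baseline stratification factors as covariates". Time to symptom alleviation has the same adjusted Cox model for its hazard ratio and interval. The only Cox code, Appendix 2, item 25, is "model aval*cnsr(1) = trt01p strat1 strat2 strat3 /risklimits = wald".

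**Rules on strata and status.** SAP 3.3 lists the randomization factors as region (US or not), age (under 60, or 60 and over) and skilled nursing facility residence. It asks for a stratified analysis of the primary endpoint and is silent on the secondary ones. SAP 3.5 treats every efficacy endpoint other than the primary as exploratory, tested at two-sided 5% without adjustment. Protocol 8.5.2 allows a Wilcoxon test or an analysis of variance model for continuous endpoints and names no covariates.

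**The concern.** Stratified randomization balances the arms on the three factors. If those factors predict the outcome, the treatment estimate already benefits from that balance, but a model that omits them leaves their variance in the residual. The reported standard error is then too large, the interval too wide, and the test rejects less often than 5% under the null. Some precision that the design has already paid for is not used.

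DAVG7 is the listed secondary endpoint for the antiviral-activity objective, and enrollment stopped at 584 randomized of 1264 planned (SAP 2.1.1). Inexpensive precision is therefore worth having. The factors already exist as analysis variables in item 25, and the SAP gives no reason for using them in the Cox models but not here.

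**Working it through.** **1. Count of models.** The visible text of SAP 6.2.1 has six regression models: Cox for three composites, for hospitalization and for alleviation, and one ANCOVA. Five carry the factors and one does not.

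**2. No figure to reproduce.** The documents give no power, SD, effect size or sample size for DAVG7. The following are assumptions:
- n of 300 to 584 (584 randomized is the upper bound);
- strata with one-third aged 60 or over, 10% ex-US and 3% in nursing facilities;
- partial R² of the three factors, given treatment and baseline viral load, of 0 to 10%, split 60/30/10 between age, region and nursing facility;
- an effect giving 80% power when the factors explain nothing.

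**3. Size of the standard error.** Without the factors it is larger by 1/√(1−R²):
- R² 1%: 1/√0.99 = 1.005
- R² 5%: 1/√0.95 = 1.026
- R² 10%: 1/√0.90 = 1.054

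**4. Power and null rejection.** With the factors, power is Φ[(1.960+0.842)/√(1−R²) − 1.960]. Without them, under exact balance, the estimate has the smaller variance but is judged against the larger standard error, so power is Φ[0.842/√(1−R²)] and null rejection is 2Φ[−1.960/√(1−R²)].

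| R² | Power without | Power with | Gain (points) | Null rejection without |
|---|---|---|---|---|
| 1% | 80.1% | 80.4% | 0.3 | 4.9% |
| 5% | 80.6% | 82.0% | 1.4 | 4.4% |
| 10% | 81.2% | 84.0% | 2.7 | 3.9% |

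Simulation with permuted blocks of 4 in eight strata (8000 trials per row; Monte Carlo SE 0.45 points per power figure) gives gains of 0.1, 1.7 and 2.9 points at n=500, and 0.2, 1.5 and 2.8 at n=300. Across simulation runs, null rejection without the factors was 4.0% to 4.7% at R² 5% and 3.4% to 4.2% at R² 10%. With the factors it was 4.3% to 5.4%.

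**5. Cost if the factors explain nothing.** Three residual degrees of freedom are spent. If the sample R² is exactly zero, the standard error grows by √[(n−3)/(n−6)]: √(297/294) = 1.005 at n=300 and √(581/578) = 1.003 at n=584. If R² is zero in the population, chance association repays nearly all of this; the simulated increase is 0.03% to 0.08%, or 0.07% to 0.13% after 15% random exclusions.

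**6. What these R² values require.** A factor with prevalence p that carries a share f of R² needs a mean shift of √[f·R²/(p(1−p))] residual SDs.
- R² 10%: age √(0.06/0.2222) = 0.52; region √(0.03/0.09) = 0.58; nursing facility √(0.01/0.0291) = 0.59
- R² 5%: 0.37, 0.41 and 0.41
- R² 1%: 0.16, 0.18 and 0.19

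The treatment effect giving 80% power is 2 × 2.802/√n: 0.25 SD at n=500 and 0.32 SD at n=300. At n=500, the 10% case makes each factor more than twice the treatment effect, and the 5% case about one and a half times.

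**The case against.** **The ANCOVA is not the odd one out among tests.** SAP 6.2.1 has eight between-arm comparisons: three adjusted Cox models, two Fisher tests (mortality, oxygen), two log-rank tests with no strata named (hospitalization, alleviation) and the ANCOVA. Five of the eight ignore the factors. This stands: the contrast holds for regression models only, and only in the visible text, because the material after the DAVG7 paragraph is redacted and could contain a stratified supplementary analysis.

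**No rule is broken and the gain is unknown.** Both stand. Protocol 1.3 links age to adverse outcomes, not to viral-load change given baseline. Step 6 shows that a gain of a few points needs large factor effects, so the likely gain is small. This does not remove the case for the change, because the cost is close to zero and the type I error is not put at risk.

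**A reader might infer more from the log-rank tests.** For alleviation, "log-rank test will be used to compare treatment groups for the time to alleviation of baseline COVID-19 symptoms", while the hazard ratio and interval come from an adjusted Cox model; hospitalization is handled in the same way. It is tempting to conclude that those p-values should also be replaced by adjusted Cox p-values. The documents do not support that. Protocol 8.5.2 names the log-rank test for hospitalization and for time-to-first-event endpoints, and no consistent gain can be shown. Item 25 is the only Cox code and matches the primary model, so a change to its tie handling made there would also alter the primary analysis.

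**Conclusion.** The point holds as an optional precision improvement. The planned ANCOVA is valid and contradicts nothing in the SAP. If the factors predict viral-load change it is mildly conservative; it does not inflate type I error, and a reader should not take the omission as bias or as a breach of SAP 3.3.

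The simulated benefit is about 0 to 0.2 power points at a partial R² of 1% and about 1.5 to 3 points at 5% to 10%, against a standard error at most about 0.5% larger if the factors explain nothing. The R², the stratum shares and the size of the Virology Analysis Set are all assumed. The direction of the benefit and the near-zero cost do not depend on their exact values; the size of the benefit does.

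**What to change.** Make the change before unblinding.

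- **SAP 6.2.1:** state that DAVG7 is analysed by ANCOVA with baseline viral load and the three stratification factors as covariates.
- **Appendix 2, item 15:** use `class trt01pn strat1 strat2 strat3; model DAVG = trt01pn base strat1 strat2 strat3 / solution; lsmeans trt01pn / stderr cl pdiff om;`. The `om` option (observed margins) stops the arm-level least-squares means from giving nursing-facility residents and non-residents equal weight; the treatment difference is unaffected.
- **SAP 6.4:** add one sentence recording the ANCOVA covariates. Protocol 8.5.2 names none, and 6.4 at present lists only the oxygen endpoint as changed.

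The cost is three SAS statements and two short text edits. The variables `strat1` to `strat3` are already used in item 25, so no new derivation or data are needed. Leave item 25 and the log-rank tests as they are.
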